3.7.2.3.2 Vital Signs (Body Temperature, Blood Pressure, Pulse Rate)

Vital signs will be measured at scheduled time points.

1) Body temperature

Axillary temperature will be measured in tenths of a degree Celsius and documented together with the date and time of measurement in source documents and the CRF.

Protocol 156-102-00136

2) Blood pressure (diastolic and systolic), pulse rate

Blood pressure and pulse rate will be measured after the subject has rested in the sitting position for at least 3 minutes and documented together with the date and time of measurement in source documents and the CRF.

3.7.2.4 Electrocardiogram Assessments

A 12-lead electrocardiogram will be obtained at scheduled time points after the subject has rested in the supine position for at least 5 minutes. Heart rate, RR interval, PR interval, QRS interval, QT interval, and corrected QT interval (Fridericia's correction, QTcF; Bazett's formula, QTcB) will be measured. The investigator or subinvestigator will evaluate the ECG data and documents them together with the date and time of measurement, normal/abnormal assessment, and other findings in source documents and the CRF.

3.7.2.5 Body Weight

The subject's body weight will be measured to 0.1 kg at scheduled time points. The body weight value will be documented together with the date and time of measurement in source documents and the CRF.

3.7.3 Pharmacokinetic Assessments

3.7.3.1 Time Points

Cohort 1 and 2: Before IMP administration and 1, 2, 3, 4, 5, 6, 8, 10, 12, and 16 hours postdose in each period

[Rationale for blood collection time points]

A single oral dose study (156-00-001), food effect study (156-00-002), oral repeated-dose study (156-00-003), and food effect study using the finished product (156-07-002) have been completed in Japan. In these studies, the mean t_{max} and mean elimination half-life were 2.18 to 3.21 hours and 3.33 to 4.39 hours, respectively, after dosing of 15 mg and 30 mg tablets. The studies also reported the linearity of tolvaptan pharmacokinetics (excluding C_{max}) in the dose range of 5 to 480 mg,⁴ suggesting a similar half-life for the 15 mg and 30 mg tablets. The time period at least 3 times the sum of t_{max} + elimination half-life, calculated based on the data from the above 4 studies (as recommended for calculation of a biological fluid sampling time point in the Guidelines for Bioequivalence Studies of Generic Products¹) was not less than 16 hours. Based on the above, the 11 time points (immediately before dosing, 4 points around the t_{max} [1, 2, 3, and 4 hours postdose], and 6 points in the elimination phase [5, 6, 8, 10, 12, and 16 hours postdose]

Protocol 156-102-00136

were selected for each period with reference to the Guidelines for Bioequivalence Studies of Generic Products.¹

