1.2.1 Single Oral Dose Study (156-00-001)

OPC-41061 15 to 120 mg was administered once orally to 40 healthy adult male volunteers under fasted conditions.

1) Pharmacokinetic Results

- Plasma pharmacokinetics of OPC-41061 after dosing of 15 to 120 mg showed large inter-individual variability. DM-4103 showed the highest plasma concentration (C_{max} and AUC_t) and is therefore considered the primary metabolite of OPC-41061. Among OPC-41061 metabolites, MOP-21826 was consistently below the lower limit of quantitation throughout the study period in all subjects (treated with 60 mg or 90 mg).
- The AUC_t and C_{max} of OPC-41061 showed a fairly dose-dependent increase without obvious nonlinear changes as the dose increased (15 to 120 mg). Statistical evaluation confirmed dose proportionality (linearity) in AUC_t but not in C_{max} . The $t_{1/2,z}$ of OPC-41061 was prolonged as the dose increased. The mean $t_{1/2,z}$ in the 120 mg group was about 3 times that in the 15 mg group (9.33 hours vs 3.33 hours).
- The cumulative urinary excretion of OPC-41061 had mostly reached plateau by 48 hours postdose in all subjects. The fe_{48h} of OPC-41061 was less than 1% in all subjects, indicating urine excretion does not account much for elimination of OPC-41061 from the system. Among metabolites, urinary concentrations of DM-4103, DM-4105, and MOP-21826 were consistently below the lower limit of quantitation in all subjects treated with 60 mg or 90 mg.

2) Pharmacological Results

- Twenty-four-hour cumulative urine volume dose-dependently increased, and, in the highest dose (120 mg) group, it reached 11945.8 mL, approximately 4.6 times that in the placebo group. The urine excretion rate until 8 hours postdose (urine was pooled in 2-hour periods until 8 hours postdose) increased to approximately 700 to 800 mL/h (in 60 to 120 mg groups). It subsequently decreased, but diuretic effects were observed until 24 hours postdose in the 60 to 120 mg groups.
- No marked increase or dose-dependent change was observed in 24-hour cumulative urine sodium excretion. Twenty-four-hour cumulative urine potassium excretion increased with dose.
- Urine osmolality decreased from immediately after dosing (from the interval of 0 to 2 hours postdose) accompanied by hypotonic urine and a high positive value for free water clearance from immediately after dosing. These water diuretic effects lasted longer at higher dose levels.

Protocol 156-102-00136

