3.2.2 Treatment Period

After single oral dosing in Period 1, there is a 72-hour washout period, followed by single oral dosing in Period 2 (different from the formulation + regimen combination in Period 1). After single oral dosing in Period 2, there is a 72-hour washout period, followed by single oral dosing in Period 3 (different from the formulation + regimen combination in Periods 1 and 2).

[Rationale for treatment period and washout period]

Treatment period: according to the statement in the Guidelines for Bioequivalence

Studies of Generic Products,¹ “In principle, bioequivalence studies should have a single-dose design.”

Washout period:

In the single oral dose study (156-00-001), food effect study (156-00-002), and single-dose part of the oral repeated-dose study (156-00-003) conducted in Japan, the mean elimination half-life of tolvaptan after administration of 30 mg was 3.89, 4.39 (in a fasting state), and 3.33 hours, respectively. Guidelines for Bioequivalence Studies of Generic Products¹ state “Washout periods should usually be more than 5 times the elimination half-life of the unchanged active ingredient or active metabolites to be measured.” The longest reported elimination half-life in these studies was 8.5 hours (Study 156-00-002, Subject No. 001-0016). At least 5 times 8.5 hours means the washout period should be at least 43 hours. Plasma tolvaptan concentration at 48 hours postdose was below the lower limit of quantitation (5 ng/mL) in all subjects enrolled in the above 3 studies. Because 2 ng/mL is being adopted as the lower limit of quantitation in the present study, 72 hours is selected for washout to ensure plasma tolvaptan concentration decreases to sufficiently low levels between doses to ensure accurate bioequivalence evaluation.

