9.2 Statistical Analysis of Reference Variables

For the AUC_{∞} , MRT_{∞} , t_{max} , and λ_z of tolvaptan, data (excluding t_{max}) will be log-transformed and analysis of variance (ANOVA) will be performed using group (group receiving conventional tablet first, group receiving OD tablet without water first, and group receiving tolvaptan OD tablet with water first), formulation and dosing regimen, subjects within group, and administration period (Period 1, Period 2, and Period 3) as factors. The analysis will use natural logarithms. The effects of the formulation and dosing regimen will be analyzed at a significance level of 5%.

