9.3 Methods of Pharmacokinetic Analysis

9.3.1 Blood Collection Time Points

In each period, before IMP administration and 1, 2, 3, 4, 5, 6, 8, 10, 12, and 16 hours postdose

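### Does the protocol's own sampling rule show that a last blood sample at 16 hours is too early?

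*Protocol*

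**What the plan says.** Protocol 3.7.3.1 (Time Points) schedules samples before dosing and at ten times from 1 to 16 h after it. SAP 9.3.1 repeats this: "In each period, before IMP administration and 1, 2, 3, 4, 5, 6, 8, 10, 12, and 16 hours postdose". The rationale draws on four earlier Japanese studies, with mean tmax of 2.18 to 3.21 h and mean half-life of 3.33 to 4.39 h for the 15 mg and 30 mg tablets. It then gives the guideline rule as "The time period at least 3 times the sum of t_{max} + elimination half-life, calculated based on the data from the above 4 studies" and reports that the result "was not less than 16 hours". It also argues from linear pharmacokinetics, "suggesting a similar half-life for the 15 mg and 30 mg tablets".

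Three other places bear on the point:

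- Protocol 3.2.2 (Treatment Period), the washout rationale, covers three of the four studies: "the mean elimination half-life of tolvaptan after administration of 30 mg was 3.89, 4.39 (in a fasting state), and 3.33 hours, respectively". It adds: "The longest reported elimination half-life in these studies was 8.5 hours".
- Protocol 1.2.1, on study 156-00-001, says that the half-life "of OPC-41061 was prolonged as the dose increased", from 3.33 h at 15 mg to 9.33 h at 120 mg.
- SAP 9.2, on reference variables including AUC to infinity, states: "The effects of the formulation and dosing regimen will be analyzed at a significance level of 5" per cent. SAP 9.1 specifies ratios with 90% confidence intervals for AUCt and Cmax only.

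**The concern.** AUCt is one of the two primary variables, and the last sampling time limits how much of the curve it can cover. The only stated reason for 16 h is the rule in 3.7.3.1. Worked through as printed, the rule asks for more than 16 h at every combination of the stated means. A reader could conclude that the sampling window fails the criterion cited for it, and that AUCt is cut short for slow eliminators.

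Three further points seem to add weight. The washout was set from the longest individual half-life, while the sampling rationale uses means. The half-life is called similar at 15 mg and 30 mg although study 156-00-001 found it rising with dose. And AUC to infinity, the natural check on truncation, is given a 5% test with no stated model-based ratio and 90% interval. If truncation hid a real difference between formulations, bioequivalence could be declared wrongly.

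**Working it through.** **Inputs.** Mean tmax 2.18 to 3.21 h and mean half-life 3.33 to 4.39 h (Protocol 3.7.3.1). Mean half-lives at 30 mg: 3.89 h (156-00-001), 4.39 h (156-00-002, fasting) and 3.33 h (156-00-003); longest individual half-life 8.5 h (all Protocol 3.2.2). Last sample 16 h.

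**1. The rule as printed, 3 × (tmax + half-life).**

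- 3 × (2.18 + 3.33) = 16.53 h
- 3 × (3.21 + 3.33) = 19.62 h
- 3 × (2.18 + 4.39) = 19.71 h
- 3 × (3.21 + 4.39) = 22.80 h

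The plan's statement is reproduced as an inequality, since all four values are at least 16 h. For the same reason a 16 h sample falls short of the rule, by 0.53 to 6.80 h. This holds however tmax and half-life pair up by study.

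**2. The other reading, tmax + 3 × half-life.** The range runs from 2.18 + 3 × 3.33 = 12.17 h to 3.21 + 3 × 4.39 = 16.38 h. The other two corners are 13.20 h and 15.35 h. A 16 h sample covers three corners and misses the fourth by 0.38 h, about 23 minutes.

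**3. By study, tmax anywhere in the stated range.**

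| Study | Half-life (h) | 3 × (tmax + half-life) | tmax + 3 × half-life |
|---|---|---|---|
| 156-00-001 | 3.89 | 18.21 to 21.30 h | 13.85 to 14.88 h |
| 156-00-002 | 4.39 | 19.71 to 22.80 h | 15.35 to 16.38 h |
| 156-00-003 | 3.33 | 16.53 to 19.62 h | 12.17 to 13.20 h |

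On the second reading, a result of at least 16 h is possible only in 156-00-002, and only with a mean tmax of at least 16 − 3 × 4.39 = 2.83 h. The fourth study's half-life is not given separately. So neither reading fits perfectly: the first makes the sentence true but unhelpful, the second makes 16 h about right but the sentence true in at most one of these three studies.

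**4. What the window does to AUCt.** Assumption: a one-compartment model with first-order absorption, the absorption rate solved from tmax and half-life.

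| Half-life (h) | AUC to 16 h as share of total (tmax 2.18 / 3.21 h) | AUC to 16 h ratio if absorption is 25% slower |
|---|---|---|
| 3.33 | 95.3% / 93.3% | 0.994 / 0.978 |
| 3.89 | 92.9% / 91.0% | 0.993 / 0.980 |
| 4.39 | 90.5% / 88.7% | 0.993 / 0.981 |
| 8.5 (one individual) | 71.2% / 69.7% | 0.991 / 0.983 |

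The last column has a true AUC-to-infinity ratio of 1, so it isolates the effect of truncation: 0.6 to 2.2% at the mean half-lives and 0.9 to 1.7% at 8.5 h. The acceptance range is 0.80 to 1.25. If the formulations differ only in the amount absorbed, both curves scale by the same factor and the AUC ratio to 16 h equals the ratio to infinity.

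**5. Half-life by dose.** The mean is 3.33 h at 15 mg (Protocol 1.2.1) and 3.33, 3.89 and 4.39 h at 30 mg (Protocol 3.2.2). Within 156-00-001 the step from 15 to 30 mg is 3.89 / 3.33 = 1.17. The 9.33 h value belongs to 120 mg, a dose not given in this trial.

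**The case for a change.** The strongest case for acting is that the rationale concerns a primary variable, cannot be reproduced from its own inputs, and would cost only wording to mend. A misprint does not fully explain it either, because on the second reading the stated result fits at most one of the three studies that can be checked. All of that stands. It concerns the explanation of the schedule; nothing in it changes a sample, an estimate or the bioequivalence criterion.

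The supporting arguments are weaker.

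- **AUC to infinity.** It is not true that truncation could not be examined. SAP 6.2 and 9.3.2 plan by-subject ratios of both AUCt and AUC to infinity for each OD regimen against the conventional tablet. SAP 9.4.2 adds geometric means of both and descriptive statistics for the extrapolated percentage. Only a model-based AUC-to-infinity ratio with a 90% interval is unstated, and the SAP's list of tables, which might include one, is not in the text available.
- **The 5% test.** Borrowing the AUCt variance of 0.033 (Protocol 7.1, read as log-scale within-subject variance) for AUC to infinity, with 42 subjects, the standard error is √(2 × 0.033 / 42) = 0.0396. With t = 1.990 on 80 degrees of freedom, only estimated ratios outside 0.924 to 1.082 are significant. But in the slower-absorption scenario the AUC-to-infinity ratio is truly 1, so a non-significant result is the correct one.
- **Washout against sampling.** Washout has to protect each subject from carry-over, so the longest individual half-life is the right input there. A sampling rule worked from study-level data serves a different purpose. The 70 to 71% coverage pairs one subject's half-life, from a food-effect study with the food state not stated, with study-mean tmax values.
- **Similar half-lives.** The 15 mg mean equals one of the three 30 mg means, so the claim holds for the two doses used, even if linearity is a weak reason for it.

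**Conclusion.** The concern does not lead to a change. What stands is an unclear sentence in Protocol 3.7.3.1: the rule as printed yields 16.53 to 22.80 h and so does not support a 16 h endpoint, while tmax plus three half-lives yields 12.17 to 16.38 h and supports it to within 0.38 h. The cited guideline is not available here, so which formula was meant remains open.

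The consequence for the bioequivalence conclusion is negligible on either reading. Truncation at 16 h shifts the AUCt ratio by about 2% at most, even if one formulation is absorbed 25% more slowly, and leaves a difference in extent intact. These figures rest on the one-compartment assumption and the protocol's mean tmax and half-life ranges; per-study tmax values are not given. The planned extrapolated percentages and AUC-to-infinity summaries will show how much of the curve was missed. A 16 h last sample is a fair trade-off with an imprecisely worded reason behind it.

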3.7.3.2 Blood Collection Procedure and Sample Treatment

About 4 mL of blood will be drawn each time from a vein and collected in a sodium heparin tube. The date and time of each blood collection will be recorded in source documents and the CRF.

After collection, the tube will be gently inverted a few times and placed in ice water. Then the sample will be immediately (within 45 minutes after collection) centrifuged at about 4°C and about 1710 × G for about 10 minutes. The separated plasma will be divided into 2 polypropylene sample tubes in nearly equal volumes and frozen at -15°C or lower within about 90 minutes after separation. A sample label on which essential information (protocol number, subject identifier, time of sampling, etc.) is entered at the trial site will be affixed to each plasma sample tube.

3.7.3.3 Transportation

Plasma samples will be kept frozen with dry ice and sent to the bioanalytical laboratory. Two samples obtained at one time point from one subject will be sent in separate shipments to the bioanalytical laboratory.

3.7.3.4 Plasma Drug Concentration Measurement

Plasma tolvaptan concentration will be determined at the bioanalytical laboratory according to the validated procedure at the laboratory.

3.7.3.5 Reporting of Measurement Results

The bioanalytical laboratory will retain the source documents of plasma drug concentration measurements. The sponsor will keep the copy of electronic file of plasma drug concentration measurements submitted by the bioanalytical laboratory.

3.7.3.6 Handling of Remaining Samples

The bioanalytical laboratory will keep remaining samples frozen and dispose of them after completion of the clinical study report.

3.7.4 End of Trial

The end of trial date is defined as the day on which the last subject completes the trial.

Protocol 156-102-00136

3.8 Stopping Rules, Withdrawal Criteria, and Procedures

3.8.1 Entire Trial

If the sponsor terminates or suspends the trial for safety or any other unexpected reason, prompt notification will be given to the head of the trial site and regulatory authorities in accordance with regulatory requirements.

3.8.2 Individual Site

Individual trial site participation may be discontinued by the sponsor, the investigator, or the IRB if judged to be necessary for medical, safety, regulatory, ethical or other reasons consistent with applicable laws, regulations, and GCP. The head of the trial site will notify the sponsor promptly if the trial is terminated by the investigator or the IRB at the site.

3.8.3 Individual Subject Discontinuation

3.8.3.1 Treatment Discontinuation

After IMP administration, a subject may stop treatment permanently for a variety of reasons. Treatment discontinuations may be initiated by a subject or may become medically necessary due to adverse events (AEs), required treatment with a disallowed medication or therapy, or other issues, as determined by the investigator. The discontinued subject should be encouraged to undergo the examinations specified for discontinuation.

3.8.3.2 Documenting Reasons for Treatment Discontinuation

All subjects have the right to withdraw their consent from further participation in the trial at any time. The investigator can also discontinue a subject's participation in the trial at any time if medically necessary. The subject's participation in the trial must be terminated when any of the following applies:

- Reasons related to AE:
 - Subject decides to discontinue because of annoyance or discomfort due to a non-serious AE which is not otherwise determined to be an undue hazard
 - Continuing IMP places the subject at undue risk as determined by the investigator (eg, a safety concern that is possibly, probably, or likely related to IMP)
 - Serious adverse event (SAE)
 - Other potentially IMP-related safety concerns or AEs
- Death
- Reasons unrelated to medical condition (provide detail and review AE history with subject)

Protocol 156-102-00136

- Withdrawal of informed consent (complete written withdrawal of consent form)
- Lost to follow-up
- Termination of all or part of the trial by the sponsor

If the subject (temporarily interrupts or) discontinues IMP due to an AE, the investigator will follow the event until it has resolved or stabilized according to [Section 5.7, Follow-up of Adverse Events](#).

3.8.3.3 Withdrawal of Consent

All subjects have the right to withdraw their consent from further participation in the trial at any time without prejudice. Subjects cannot withdraw consent for use of data already collected as part of the trial, but only for future participation.

Withdrawal of consent is a critical trial event and therefore should be approached with the same degree of importance and care as is used in initially obtaining informed consent. The reasons for a subject's intended withdrawal need to be completely understood, documented, and managed to protect the rights of the subject and the integrity of the trial.

A subject who withdraws consent should be encouraged to undergo the examinations specified for discontinuation.

3.9 Screen Failures

A screen failure subject is one from whom informed consent is obtained and is documented in writing (ie, subject signs an ICF), but who is not started on treatment.

Subjects who sign an ICF but who are not started on treatment are permitted to be re-screened. In the event that the subject is re-screened for trial participation, and the re-screening is not completed within the original screening window, a new ICF must be signed.

3.10 Definition of Completed Subjects

The treatment period is defined as the time period during which the subject is evaluated for primary and/or reference objectives of the trial irrespective of whether or not the subject received all doses of the IMP. Subjects who undergo the last scheduled evaluation during the treatment period will be defined as trial completers. For purposes of this trial, subjects who complete the evaluation in Period 3 will be defined as trial completers.

Protocol 156-102-00136

3.11 Definition of Subjects Lost to Follow-up

Subjects who cannot be contacted after discharge in Period 3 will be classified as “lost to follow-up.”

The investigator or designee will make 3 documented attempts to contact the subject by telephone and in the event the site is unable to reach the subject by telephone, the site will attempt to contact the subject via certified mail or an alternative similar method, where appropriate, before assigning a “lost to follow-up” status.

3.12 Subject Compliance

The subject should be under the supervision of the investigator during the trial. The investigator will guide the subject so that the subject complies with the restrictions specified in [Section 4, Restrictions](#).

3.13 Protocol Deviations

In the event of a significant deviation from the protocol due to an emergency, accident, or mistake (eg, violation of informed consent process, IMP dispensing or subject dosing error, treatment assignment error, subject enrolled in violation of eligibility criteria or concomitant medication criteria), the investigator or designee will contact the sponsor at the earliest possible time by telephone. The investigator and sponsor will come as quickly as possible to a joint decision regarding the subject’s continuation in the trial. This decision will be documented by the investigator and the sponsor, and reviewed by the site monitor.

4 Restrictions

4.1 Prohibited Medications

If the subject uses any drug other than the IMP between the time of consent and the end of treatment examination in Period 3 or discontinuation, the name, purpose of use, regimen, dose, route, and start and end dates (and time if possible) will be documented in source documents and the CRF. If the subject undergoes any non-drug therapy during the same period, its name, purpose, and start and stop dates will be also documented in source documents.

When the subject needs a prohibited drug or therapy to eliminate immediate hazards to the subjects (eg, for the treatment of AEs), the subject is to terminate the trial according to [Section 3.8.3, Individual Subject Discontinuation](#).

Protocol 156-102-00136

Prohibited medication/therapy	Restricted period
Any prescription and OTC drug other than the IMP	Between 14 days before IMP administration in Period 1 and discharge in Period 3
Any non-drug therapy	During hospitalization

